# Definition of the primary effectiveness endpoint, total clinical condom failure rate:

The probability of total clinical condom failure is defined as the number of condoms that break or slip completely off the penis during intercourse or correct withdrawal as a proportion of the condoms used for vaginal intercourse.

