### Consent/Instruction (SV1)

The consent visit (SV1) will be conducted remotely via videoconference with both partners present using one video camera. Both partners will show a valid, official government-issued photo identification for verification. Research staff will show company issued photo identification. Couples will receive information about the study and each partner will receive an electronic informed consent. Each couple will complete informed consent procedures, including electronically signing an informed consent form, prior to completing any study procedures. The original signed informed consent will also be signed by the research staff member conducting the

consent visit and an electronic copy of the signed consent will be provided to each subject. The fully signed informed consent will be kept on file by the investigator.

If for any reason it is not possible to sign the consent forms electronically, a facsimile or photographic image of the signed form may be sent through electronic means providing all other conditions of the Protocol are met. Alternatively, the signed consent form may be scanned and returned through a specified e-mail account, or posted to a specified internet address. Study subjects may bring the signed and dated consent form to the clinical site or Curbside meeting location, if restrictions on traveling to the Clinical Study site are alleviated, or send it to the clinical investigator by trackable/signed receipt mail. No study procedures may be conducted until the signed consent form is received, has been signed by the research staff member who conducted the consent visit, and a copy of the signed form has been provided to the subject.

After signing the informed consent, both partners will view a video which will demonstrate the correct way to don (teat up position) and remove condoms. Couples will be instructed that the penis should be withdrawn completely soon after ejaculation, while holding the condom firmly in place at the base of the erect penis (ISO 23409:2011 clause 6.2.3.3.d). Couples will be encouraged to ask questions to demonstrate their comprehension of the instructional video and research staff will help to clarify any unclear directions. Research staff will instruct couples on how to take penis measurements using a penis measurement kit. Intensive instruction will also be given on completing all self-administered data collection forms.

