# Observations contributing to the analyses

Condoms used for vaginal intercourse will be included in the analysis with the following exceptions:

- 1. Condoms used for anal intercourse during the same act.
- 2. Condoms used during oral sex during the same act.
- 3. Condoms exposed to mouth or genital jewelry.
- 4. Condoms used other than with the supplied Astroglide™ lubricant.
- 5. Condom packages opened with sharp objects or teeth.
- 6. Condoms that slipped completely off the penis when not held at the base of the erect penis during withdrawal

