### Additional Analyses

Functionality measures (including measure that will be included in the primary effectiveness endpoint of total clinical failure)

The analysis will include the calculation of the following functionality measures for both condom types. These will be reported as probabilities including 95% confidence intervals.

Nonclinical failure: Number of condoms that could not be used because of breaks,

donning problems, or defect over the number of condoms

opened for use

Clinical breakage: Number of condoms that broke during intercourse over

the number of condoms used for vaginal intercourse (clinical breakage will be included in the primary effectiveness endpoint

of total clinical failure)

Complete slippage Number of condoms that slipped completely (100%) off the

erect penis during intercourse or on correct withdrawal over the number of condoms used for vaginal intercourse. (Condoms that slip completely (100%) off the penis during withdrawal when neither partner held the condom at the base

of the erect penis during withdrawal are excluded.)

Slippage during intercourse: Number of condoms that slipped off penis during intercourse

over the number of condoms used for vaginal intercourse

Slippage during withdrawal: Number of condoms that slipped off penis during withdrawal

over the number of condoms used for vaginal intercourse.

Partial slippage: Number of condoms that slipped off penis during withdrawal

over the number of condoms used for vaginal intercourse.

Total failure: Number of condoms that broke during package opening,

donning, intercourse or correct withdrawal, or slipped off the penis during intercourse or correct withdrawal or could not be used (donning problems or defect) over the number of condoms

opened for use.

Total slippage: Number of condoms that slipped off penis during intercourse or

correct withdrawal over the number of condoms opened for use (total slippage will be included in the primary effectiveness

endpoint of total clinical failure)

Other failure: Number of condoms that could not be used due to donning

problems or defect over the number of condoms opened for use

We will also assess the association between penis size and breakage/slippage for each condom type e.g., whether increased or decreased rates for total clinical failure, clinical breakage and total slippage as a function of penis size.

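### The endpoint definitions treat breaks at withdrawal inconsistently; read naturally, they leave a break at a not-held withdrawal in the denominator as a non-failure

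*Combined protocol and SAP*

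**What the plan says.** All places are in the Combined protocol and SAP.

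- **Section VI, definition of the primary effectiveness endpoint.** The numerator is "the number of condoms that break or slip completely off the penis during intercourse or correct withdrawal", taken "as a proportion of the condoms used for vaginal intercourse".
- **Section VI, Observations contributing to the analyses.** The default is to keep every vaginal use: "Condoms used for vaginal intercourse will be included in the analysis with the following exceptions". Six exceptions follow. The only one about withdrawal is the sixth: "Condoms that slipped completely off the penis when not held at the base of the erect penis during withdrawal". It does not mention breaks.
- **Section VI, Additional Analyses, Functionality measures.** Clinical breakage, which the entry says is part of the primary endpoint, is the "Number of condoms that broke during intercourse over" the condoms used for vaginal intercourse. It does not mention withdrawal. Total failure begins "Number of condoms that broke during package opening" and goes on "donning, intercourse or correct withdrawal, or slipped off the" penis, so it applies the correct-withdrawal condition to breaks. Complete slippage repeats the not-held exclusion, for slips only.
- **Section II, Consent/Instruction (SV1).** Couples are told to withdraw "while holding the condom firmly in place at the base of the erect penis". This is what gives correct withdrawal its meaning.

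No section says how to code a break during a withdrawal where the condom was not held.

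**The concern.** Whether the base was held bears on slippage, so it is a sensible condition for a slip. The plan gives no reason to discount a break on that ground. Yet the wording appears to do so, and more leniently than for slips: a complete slip at a not-held withdrawal leaves both numerator and denominator, while a break in the same circumstances stays in and counts as a condom that worked.

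At stake is whether real failures drop out of the primary endpoint of a non-inferiority trial. If such breaks were more frequent with a test condom than with the control, the observed difference would be too small. The test condoms are 0.024 and 0.018 mm thick against 0.055 mm for the control (section IX), so unequal breakage is worth guarding against, although the documents give no breakage rates by type.

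**Working it through.** **Step 1. Apply the rules case by case.** Natural reading of the primary definition, assuming exceptions 1 to 5 do not apply:

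| Event in a vaginal use | In numerator? | Exception 6? | Result |
|---|---|---|---|
| Break during intercourse | yes | no | failure |
| Break at held withdrawal | yes | no | failure, but outside Clinical breakage as worded |
| Break at not-held withdrawal, no slip | no | no | stays in denominator as non-failure |
| Complete slip at not-held withdrawal | no | yes | removed |
| Break during intercourse, then complete slip at not-held withdrawal | yes | yes | removed, although it broke |

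Row 3 is the main gap. Row 2 shows that Clinical breakage disagrees with the endpoint it feeds, unless intercourse is meant to include withdrawal. Row 5 shows that exception 6 can remove a real break.

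**Step 2. Reproduce the plan's power.** The plan states no figure for this point, but its power inputs give the standard error used below. From section VI, Sample Size Justification: failure rate 4%, correlation ρ = 0.2, Z = 5 condoms per type, margin 2.5 points, multiplier 1.960, and 1,275 uses per type, which is 255 couples × 5. I take Pt = Pc = 0.04, so P(1 − P) = 0.0384.

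- Var = 2 × 0.0384 × (1 + 4 × 0.2)/5 − 2 × 0.2 × 0.0384 = 0.027648 − 0.015360 = 0.012288
- SE = √(0.012288/255) = 0.00694, or 0.694 points
- Power = Φ(0.025/0.00694 − 1.960) = 94.96%, against the stated 95%

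**Step 3. Effect of each miscoded break.** One break in 1,275 uses is 1/1,275 = 0.078 points of that type's rate. An excess of 3 or 5 such breaks on a test condom over control shrinks the observed difference by 0.24 or 0.39 points. Equal counts give zero.

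**Step 4. Plausible size (assumptions, because the documents give no rates).**

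- Suppose 5–20% of withdrawals are not held and 10–50% of breaks occur at withdrawal, with not holding equally common for all types and unrelated to breakage. The share of breaks lost is 0.05 × 0.10 = 0.5% to 0.20 × 0.50 = 10%. With illustrative breakage of 3% (test) against 1% (control), a true 2.0-point difference reads as 2.0 × 0.995 = 1.99 down to 2.0 × 0.90 = 1.80, a loss of 0.01 to 0.20 points.
- Alternatively, suppose 5–20% of withdrawals are not held and 0.5–2% of those break. The hidden rate is 0.025–0.4%, or about 0.3 to 5 uses per 1,275.

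**Step 5. Effect on the error rate.** Let the true difference, counting all breaks, be exactly 2.5 points (6.5% against 4%), and let s be the hidden excess on the test condom. The chance of declaring non-inferiority is Φ(s/SE − 1.960), with SE recomputed at Pt = 6.5% − s.

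- s = 0: 2.5%
- s = 0.10 points: SE 0.797 points, chance 3.3%
- s = 0.20 points: SE 0.793 points, chance 4.4%

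**Step 6. Count or exclude?** Take 51 recorded failures in 1,275 (4.00%) and 3 hidden breaks. Excluding those uses gives 51/1,272 = 4.01%; counting them gives 54/1,275 = 4.24%. Exclusion is almost the same as scoring them as non-failures, so the choice that matters is whether they are counted.

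**The case against.** The strongest reply is grammatical. In the primary definition, the phrase about intercourse or correct withdrawal can attach to slipping alone, and then every break counts. Exception 6 and the Complete slippage entry restrict the not-held rule to slips, which fits that parse. Total failure, where the condition clearly reaches breaks, is an additional measure with a different denominator (condoms opened for use).

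This parse is possible and cannot be ruled out. It fits poorly with Clinical breakage, a named component of the primary endpoint that is limited to intercourse, and Total failure shows that the authors do attach the condition to breaks. A primary endpoint open to two readings needs settling in any case. The plan nowhere calls such a use a success; that status comes only from applying its rules.

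A reader might also infer that a break first noticed after a not-held withdrawal is lost in the same way. The documents do not support this. The definition turns on when the condom broke, not on when the break was seen, so a break during intercourse discovered later is still a failure. No section assigns a time to breaks of unknown timing. The condom report asks when a problem was noticed, and staff clarify unclear responses.

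Finally, holding the base is an inclusion commitment, is taught by video and is recorded at each use, so not-held withdrawals may be uncommon. That supports a small effect, but it does not repair the wording.

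**Conclusion.** The inconsistency is real and minor. The three parts of section VI do not agree on breaks at withdrawal, and on the natural reading of the primary definition a break at a not-held withdrawal stays in the denominator uncounted.

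The size cannot be known from the documents. Under the assumed inputs in the first part of step 4, the difference shifts by 0.01 to 0.20 points against a 2.5-point margin. The top value needs both upper assumptions at once, together with the illustrative 3% against 1% breakage. A hidden excess of 0.20 points would raise the one-sided error from 2.5% to about 4.4%.

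A reader might conclude that the rule favours the test condoms. That follows only if a test condom has more such breaks than the control. Equal numbers cancel, and more in the control would work against the test condom. The power calculation is not affected and need not change.

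**What to change.** Before data are seen:

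1. Reword the primary endpoint definition, and both Clinical breakage and Total failure under Additional Analyses, so that a break during intercourse or withdrawal is a failure whether or not the condom was held. Keep the correct-withdrawal condition for slippage only.
2. State that exception 6 does not remove a condom that also broke.
3. Report breaks at not-held withdrawals by condom type, with a sensitivity analysis that excludes those uses.

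The cost is a few words in three definitions and one exception, plus one table and one extra run of the GEE model for each comparison. Section II, Data Collection, shows that the condom report already records breakage, when a problem was noticed and whether the base was held. No new data, visits or couples are needed.

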# Observations contributing to the analyses

Condoms used for vaginal intercourse will be included in the analysis with the following exceptions:

- 1. Condoms used for anal intercourse during the same act.
- 2. Condoms used during oral sex during the same act.
- 3. Condoms exposed to mouth or genital jewelry.
- 4. Condoms used other than with the supplied Astroglide™ lubricant.
- 5. Condom packages opened with sharp objects or teeth.
- 6. Condoms that slipped completely off the penis when not held at the base of the erect penis during withdrawal

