#### **Inclusion Criteria:**

- a. Between the ages of 18 and 45 (inclusive)
- b. Protected against pregnancy by oral contraceptives, an IUD, an implant, contraceptive injections, contraceptive patch, or sterilization (tubal ligation or vasectomy)
- c. Have home internet access, a valid personal email for each partner, ability to videoconference and use electronic signature technology
- d. Willing and able to give electronic informed consent

- e. Willing to respond to questions concerning their reproductive and contraceptive history and use of condoms via interview or self-administered questionnaires
- f. Have vaginal intercourse at least once weekly
- g. Willing to use the study products for fifteen acts of vaginal intercourse within nine weeks of study entry
- h. In a mutually exclusive monogamous relationship with their study partner for at least 6 months and be willing to remain mutually monogamous throughout study participation
- i. Both study partners have previous experience using male condoms
- j. Agree not to use any additional vaginal or sexual lubricant except the Astroglide™ product provided, if desired, supplied by the study
- k. Agree not to expose the study condoms to jewelry (hand, facial, or genital) or piercings (facial or genital) that could damage the study condoms.
- I. Agree not to use sex toys or drugs intended to enhance or diminish sexual response when using study condoms
- m. Male partner agrees to ejaculate during vaginal intercourse
- n. Agree to (or partner) hold the condom at the base of the erect penis during withdrawal
- o. Agree to return any condoms that break during use
- p. Agree to return any unopened condoms
- g. Reachable by telephone

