where  $(\hat{P}e - \hat{P}c)$  is the estimated difference in total clinical failure rates between the test and control latex condoms and SE is the standard error of the difference (Taylor ).

Taylor (ibid) provides a simple formula for estimating the standard error for paired differences in observed failure rates among study couples. This method, however, requires all couples to provide data for both condom types and does not allow for within couple correlation of failure rates (clustering). To overcome these limitations the method of Generalized Estimating Equations (GEE) will be used to estimate the regression parameters and their standard errors (Diggle et al , Taylor and Dominik ).

The primary effectiveness of the condoms will be analysed by GEE separately for each of the two polyurethane test condoms against the common control natural rubber latex male condom using the PROC GEE procedure in SAS (or R if SAS is not available to the analyst) with an identify link function and an independent working correlation structure to calculate the limits of the one-sided upper 97.5% confidence intervals for the difference in the total clinical failure rates for the test polyurethane male condoms minus the control natural rubber latex male condom.

For each separate primary analysis, couples will need to have reported use of at least one test polyurethane male condom and one control natural rubber latex male condom for vaginal intercourse. Non-use of 5 condoms of each type will assumed to be non-informative for this primary analysis. We will report the amount of missing data per condom type; explore possible confounding due to differential missing data by type; and perform a sensitivity analysis based on 'completers' (i.e., use of all 5 condoms of each type being compared). For analysis purposes missing outcome data for individual condom uses will be assumed to be missing completely at random. The potential for informative cluster sizes and resulting bias (e.g. if couples with higher

<sup>1 Taylor, Issues in the design, analysis and interpretation of condom functionality studies, Contraception 80 (2009) 237 - 244

<sup>2 Diggle, Heagerty, Laing and Zeger, Analysis of longitudinal data, 2nd ed. Oxford University Press; 2002

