<sup>3 Taylor and Dominik. Noninferiority testing and crossover trials with correlated binary outcomes and small event proportions with applications for the analysis of condom failure data, J Biopharm Statistics, 9 (2) 365 – 377 (1999)

failure probabilities use fewer condoms of either condom type) will be explored to the extent possible in sensitivity analyses. We will also assess the reasons for missing data by condom type in order to examine the assumption of randomness of missing data.

The power calculation used to determine the sample size is based on the assumption that 85% of condom uses will meet the inclusion criteria (1,275 condom uses). The 85% assumption is based on past experience of running studies of this nature. The use of a high initial power target of 95% for the calculations provides a significant level of protection against the consequences of higher than expected discontinuation rates with resulting loss of missing primary effectiveness data. If the completion rate drops to 75%, power will still exceed 90%. Even if the completion rate drops to a low as 60% the power to conclude noninferiority will remain marginally higher than 80%.

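### Minor: exception 6 drops unheld complete slips according to their outcome; the endpoint wording leaves two cases unsettled, and no planned analysis shows whether the result depends on the rule

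*Combined protocol and SAP*

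**What the plan says.** All of this is in Section VI unless stated otherwise.

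- **Endpoint definition.** Failures are condoms that break or "slip completely off the penis during intercourse or correct withdrawal as a proportion of the condoms used for vaginal intercourse". A slip at an incorrect withdrawal is not a failure, and nothing in this sentence takes the use out of the denominator.
- **Observations contributing to the analyses.** "Condoms used for vaginal intercourse will be included in the analysis with the following exceptions"; the sixth exception is "Condoms that slipped completely off the penis when not held at the base of the erect penis during withdrawal".
- **Additional Analyses, complete slippage.** A note excludes condoms that came completely "off the penis during withdrawal when neither partner held the condom at the base". It does not say whether they leave the numerator only or the denominator too.
- **Additional Analyses, withdrawal row.** "Slippage during withdrawal: Number of condoms that slipped off penis during withdrawal" carries no holding condition. The functionality rows are reported as probabilities with 95% confidence intervals and are not set against the margin.
- **Statistical Objectives.** The analyst will "perform a sensitivity analysis based on 'completers", and informative cluster size "will be explored to the extent possible in sensitivity analyses". Missing data are also reported and examined by condom type. None of this concerns holding.
- **Section II.** Couples agree to "hold the condom at the base of the erect penis during withdrawal" (inclusion criterion n), this is taught at the consent visit, and the condom report records it for each use.

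**The concern.** Two analysts could treat the same use differently. One takes exception 6 literally and deletes an unheld complete slip. The other follows the endpoint definition and keeps it as a non-failure. If the condom had also broken, the first analyst loses a failure that the second counts.

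Exceptions 1 to 5 depend on how the condom was opened or used. Exception 6 depends also on whether it failed, so an unheld use stays if nothing happened and goes if the condom came off. If condom types differ in withdrawal slippage or in how often they are left unheld, the primary difference will depart from the difference over all uses. The types do differ in flat width (58, 55 and 53 mm) and length (190, 170 and 195 mm; Section IX), so unequal slippage is possible, but the documents give no rates. A reader of the final report would see a pass or fail at 2.5% without knowing whether it rests on this rule.

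**Working it through.** **1. The plan's own figure.** Inputs from Sample Size Justification: failure rate 4% (taken as equal in both types), correlation 0.2, Z = 5, margin 2.5 points, multiplier 1.960, and 1,275 uses = 255 couples × 5.

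Var = 2 × 0.0384 × 1.8/5 − 2 × 0.2 × 0.0384 = 0.012288. SE = √(0.012288/255) = 0.694 points. Power = Φ(2.5/0.694 − 1.960) = 94.96%, against the stated 95%. The same variance formula is used below; it is not a GEE fit.

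**2. The rules side by side.**

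| Use | Endpoint definition | Exception 6, literal | All uses |
|---|---|---|---|
| Held, slipped completely off | failure | failure | failure |
| Unheld, stayed on | non-failure | non-failure | non-failure |
| Unheld, slipped completely off | non-failure | removed | failure |
| Broke, and slipped off unheld | failure | removed | failure |

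**3. Size of the effect.** Let b be failure during intercourse, s the complete slip risk at withdrawal and h the unheld share.

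- Exception 6: [b + (1−b)(1−h)s] / [1 − (1−b)hs]
- Endpoint definition: b + (1−b)(1−h)s
- All uses: b + (1−b)s

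Assumptions not in the documents: h; the same slip risk held or unheld; control b = s = 0.02 (all-uses rate 3.96%). The test values are chosen so that the all-uses difference is 2.50 points. The chance of passing is Φ((2.5 − difference)/SE − 1.960).

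Example with h = 10% and the whole excess at withdrawal (test b = 0.02, s = 0.04551): test 0.06014/0.99554 = 6.041%, control 0.03764/0.99804 = 3.771%, difference 2.270, SE 0.776, chance of passing 4.8%. By the endpoint definition the difference is 6.014 − 3.764 = 2.250.

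| Unheld share | 2% | 5% | 10% | 20% |
|---|---|---|---|---|
| Whole excess at withdrawal: difference, exception 6 | 2.454 | 2.385 | 2.270 | 2.036 |
| Same case: difference, endpoint definition | 2.450 | 2.375 | 2.250 | 2.000 |
| Chance of passing, whole excess (exception 6) | 2.9% | 3.5% | 4.8% | 9.0% |
| Chance of passing, half the excess at withdrawal | 2.7% | 2.9% | 3.5% | 4.8% |
| Chance of passing, a quarter | 2.6% | 2.7% | 2.9% | 3.4% |

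The two readings differ by at most 2.036 − 2.000 = 0.036, or about 0.04 points.

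**4. Cases with no gain for the test condom.**

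- Excess all breakage: 2.50 / 2.51 / 2.51 / 2.52 points at the four unheld shares.
- Equal rates: 0.
- Test truly 1.00 point better at withdrawal: −0.98 / −0.95 / −0.90 / −0.81.
- Equal slip risk, 10% unheld (test) against 20% (control): 0 becomes +0.19, against the test condom.

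**5. Error against the stated endpoint.** If the difference by the endpoint definition is itself 2.50 points (whole excess at withdrawal), the chance of passing under exception 6 is 2.47 / 2.42 / 2.34 / 2.16%. None exceeds 2.5%.

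**6. Constructed counts, 1,275 uses per type; bound = difference + 1.96 SE.**

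- 57 v 50 counted failures plus 6 v 2 unheld slips: 1.96 (57/1269 v 50/1273), 1.94 (57/1275 v 50/1275), 2.31 (63/1275 v 52/1275). A pass each way.
- 63 v 50 plus one unheld test slip: 2.46 (63/1274 v 50/1275), 2.45 (63/1275 v 50/1275), 2.54 (64/1275 v 50/1275). Only the all-uses bound exceeds 2.5%.
- 64 v 50 by the endpoint definition, where one of the 64 broke and also slipped off unheld: 2.54 if it counts, 2.46 (63/1274 v 50/1275) if exception 6 drops it. Here the two readings themselves fall on opposite sides of the margin.
- Planning rates, 51 v 51 (bound 1.36): counting a net excess of 13 unheld test slips gives 2.47, and 14 gives 2.55.

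**The case against.** The best reply is that nothing conflicts. One paragraph defines the endpoint and the next defines which uses enter it. Exceptions 1 to 5 also remove condoms that the endpoint wording would keep. This is the natural reading and it stands for a slip without a break. A reader might infer that the primary rate is undefined; the documents do not support that, and a clarifying clause is enough. The reply does not settle the condom that both broke and slipped off unheld.

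Second, leaving user error out is deliberate. The 2.5% margin is attached to total clinical failure as this plan defines it, and the pass chances of 2.9 to 9.0% are measured against another quantity, the all-uses difference. This also stands. A reader might infer that exception 6 inflates the false-positive rate or favours the polyurethane condoms. Step 5 shows no inflation against the stated endpoint, and step 4 shows that the effect can vanish or reverse.

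Third, every effect rests on an assumed unheld share, and holding is both a condition of entry and taught. At 2 to 5% unheld the worst case is 2.9 to 3.5% against 2.5%. The count examples that cross the margin are knife-edge, or place a net excess of 14 slips wholly in one type. That limits the weight of the point. It does not supply the missing information, because the withdrawal-slippage row is not set against the margin and may itself fall under exception 6.

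**Conclusion.** Minor. The primary rule can stand. Three things are established from the text: the treatment of an unheld complete slip is implied and not stated; a broken condom that also slipped off unheld is handled in two ways; and no planned analysis shows whether a conclusion depends on an exclusion that uses the outcome. The numerical effect is conditional on an unheld share and slip rates that the documents do not give, so neither its size nor its direction is known.

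Separately, three rows in Additional Analyses are wrong as written. Partial slippage has the same definition as slippage during withdrawal. Total slippage is said to feed the primary endpoint, yet it is divided by condoms opened and does not require the slip to be complete. Clinical breakage, also said to feed the primary endpoint, names only breaks during intercourse, whereas total failure includes breaks on correct withdrawal and the endpoint definition can be read that way.

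**What to change.** Before unmasking:

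- **(a) Supporting analysis.** Keep the primary rule. Add one supporting GEE analysis per comparison, with the model in Statistical Objectives, that retains unheld uses and counts every complete slip as a failure. Show its upper 97.5% bound beside 2.5% for reference only. Tabulate unheld uses and unheld complete slips by condom type.
- **(b) One rule.** In the endpoint definition, the exceptions and Additional Analyses, state the same treatment of an unheld complete slip. Say that a condom that broke counts as a failure even if it also slipped off unheld.
- **(c) Definitions.** Define partial slippage as slippage that is not complete. Make the slippage component of the primary endpoint complete slippage, divided by condoms used in vaginal intercourse. Align clinical breakage with the endpoint definition.

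The cost is SAP wording and two extra model runs on data already collected. Sample size and the primary decision do not change. By the plan's formula the supporting analysis would have 95.1% power at equal rates of 3.96%. Its drawback is that it includes user error which the primary endpoint omits on purpose, so a gap between the two results is not by itself evidence against a condom.
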